6.3 Secondary Outcome Measures

Utility of qER compared to standard of care:

- Time taken from acquisition to report NCCT head for patients without prioritised findings in Emergency Department
- Time taken from acquisition to report completed for patients with absence of findings on NCCT head scans in Emergency Department
- To assess impact of qER on radiology reporting workflow on other requests for CT scans
- To assess impact of teleradiology on qER supported reporting
- Time to diagnosis from CT acquisition.
- Time to referral from CT acquisition.
- Time to initiation of treatment from CT acquisition for prioritised scans.
- Death within 28 days of NCCT head acquisition
- Percentage of NCCT heads that qER classifies as prioritised and absence of findings.
- Percentage of qER non prioritised scans that radiologist identified as having prioritised finding
- Percentage of qER non prioritised but identified by radiologist as absence of finding.

Technical Evaluation of product performance:

- Sensitivity, specificity, positive and negative predictive values of qER in detecting scans with prioritized findings overall and also stratified by all 6 target abnormalities.
- Percentage of CT scans that could not be processed by qER due to technical factors.

Safety of qER:

- To assess the safety of qER of identifying patients with no prioritised findings identified on NCCT head.
- Percentage of patient NCCT Head reported incorrectly as qER non prioritised.
- Time from acquisition to reporting of CT Chest Abdo Pelvis (CAP) and Pulmonary Angiograms (CTPA) within the trust.

Health economic assessment:

- Compare costs and health benefits between pre and post implementation of qER, including cost evaluation of fully automatic diagnosis of high confidence normal triage.

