8.3 Data Collection

Evaluation sites will periodically collect, clean, link, de-identify and supply data in an agreed format, beginning with baseline data from the pre-implementation phase until the end of the post-implementation phase. The frequency of data collection is subject to change though depending on the feasibility of sites.

A data dictionary will be supplied (example included in the Appendix) that will support fulfilling these requirements from:

Extraction of routinely collected hospital data:

- Referral Data: Age, Sex, date of referral for CT, date of appointment. Where possible ethnicity and deprivation will be captured.

- Radiology Data: Number of referrals, Datetime CT acquired, Datetime CT reported, presence or absence of discordance between qER and reporting radiologist, CT device manufacturer/ type, Usual Care Report
- Clinical Data: Clinical Diagnosis, treatment initiation, referral, including date of death if applicable.
- Follow-up Data: Length of stay ED, Length of stay Hospital, Specialty pathway.
- qER data outputs from qER interpretation
- Changes in treatment pathways after implementation
- Time to diagnosis

Data linkage for follow-up (death within 28 days of Head-NCCT acquisition date) against outcomes will be collected for 28 days.

8.4 National Data opt-out.

If patient has selected National Data opt-out, their data will be excluded from final analysis.

8.5 Follow up Procedures.

Data linkage for follow-up (death within 28 days of Head-NCCT acquisition date) against outcomes will be collected 28 days after the Head-NCCT acquisition date.

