13 DATA

13.1 Data to be collected:

Evaluation sites will periodically collect, clean, link, de-identify and supply data in an agreed format, beginning with baseline data from the pre-implementation phase until the end of the post-implementation phase. The frequency of data collection is subject to change though depending on the feasibility of sites.

A data dictionary will be supplied (example included in the Appendix) that will support fulfilling these requirements from:

Extraction of routinely collected hospital data:

- Referral Data: Age, Sex, date of referral for CT, date of appointment. Where possible ethnicity and deprivation will be captured.
- Radiology Data: Number of referrals, Datetime CT acquired, Datetime CT reported, presence or absence of discordance between qER and reporting radiologist, CT device manufacturer/ type, Usual Care Report
- Clinical Data: Clinical Diagnosis, treatment initiation, referral, including date of death if applicable.
- Follow-up Data: Length of stay ED, Length of stay Hospital, Specialty pathway.
- qER data outputs from qER interpretation
- Changes in treatment pathways after implementation
- Time to diagnosis

Data linkage for follow-up (death within 28 days of Head-NCCT acquisition date) against outcomes will be collected for 28 days.

Data dictionary is attached as a separate document (Appendix 5).

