5.4.1 Pre-scan

This record type contains all attributes that are collected before a Head NCCT scan is completed for the patient in the study

| | Attribute | Data type | Mandatory | Description | Source |
|---|-----------------|-----------|-----------|---------------------------------------|----------|
| 1 | Site identifier | Varchar | Yes | The identifier allocated by the study | Assigned |

| | | | | | |
|----|--|---------------------------------|-----|--|--|
| | | | | team to the site which this patient belongs. | |
| 2 | Study patient identifier | Varchar | Yes | Unique Identification number given to each patient whose data is being analysed for the study. | Assigned |
| 3 | Patient identifier | Varchar | Yes | Unique identifies for a patient (across all sites) - likely to be conflation of site ID and site patient ID. | Assigned |
| 4 | Cohort | Varchar | Yes | The reason for having this patient in the cohort | Assigned |
| 5 | Date of Birth (DOB) | Date dd.mm.yyyy | Yes | This will determine the age of patient at time of scan | DICOM Meta Data |
| 6 | Ethnicity | Varchar | No | The likely race/ethnicity based on self-reported sources, public sources and surname/ethnicity tables. | Site specific electronic patient record |
| 7 | Gender | Numeric | Yes | Gender of the patient | DICOM Meta Data |
| 8 | Time of arrival to Emergency Department (ED) | Datetime dd.mm.yyyy hh:mm | Yes | The time of patient arrival to the Emergency Department. | Site specific electronic patient record |
| 9 | Time of triage in ED | Datetime dd.mm.yyyy hh:mm | Yes | The time of first digitally recorded clinical contact. | Site specific electronic patient record |
| 10 | Initial location cared for | Varchar | No | Where the patient was first seen. | Site specific electronic |

| | | | | | |
|--------|---|---------------------------------|-----|---|------------------------------------|
| | | | | | patient record |
| 1 1 | Indication for Head CT | Varchar | No | What did the patient present with? List 1 - Trauma; 2 - Altered focal neurology; 3 - Reduced GCS; 4 - Headache; 5 - Seizures; 6 - Other | Radiology Report. RIS - free text. |
| 1 2 | Time of CT Request | Datetime dd.mm.yyyy hh:mm | Yes | Time the clinical team requested the patient to have a head CT scan. | RIS |
| 1 3 | Does NCCT head meet qER inclusion and exclusion criteria? | Binary | Yes | Technical requirements of qER read met. | DICOM Meta Data, qER Log |

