| 13 | Discordance Review Decision: Which AI findings were accepted by the panel? | Varchar | Yes | To capture the agreement between qER and trust radiologist based on specific findings. | Derived from clinical fellow's report and qER report |
| 14 | Time of treatment related to head CT findings in ED | Datetime dd.mm.yyyy hh:mm | No | Time of intervention to treat CT Head findings. | Site specific electronic patient record |

| | | | | | |
|----|--|-------------------------------------|-----|---|---|
| | | | | | |
| 15 | Time of first intervention for critically identified scans | Datetime dd.mm.yyyy hh:mm | No | Time recorded for initial treatment option and/or referral. | Site specific electronic patient record |
| 16 | Time of discharge or referral | Datetime dd.mm.yyyy hh:mm | Yes | Electronic discharge point from ED (to ward or home). | Site specific electronic patient record |
| 17 | Length of stay in hospital | Numeric | Yes | Length of stay in hospital related to that admission. | Site specific electronic patient record |
| 18 | Was the patient enrolled in other clinical trial? | Binary | Yes | Has the patient been recruited to another study? 1 = Yes 0 = No | Site specific electronic patient record |
| 19 | If 21 = Yes; Clinical trial number [PLACEHOLDER] | Clinical trial code | Yes | The study ID if the patient is a subject? | Site specific electronic patient record |
| 20 | Patient's National Data Opt Out | Binary | Yes | If patient has selected National Data Opt out, their data will be excluded from final analysis. 1= Patient data excluded from analysis 0 = Not excluded | |

| | | | | | |
|----|--|------------------------|-----|--|---|
| | | | | | |
| 21 | Death within 28 days following discharge | Binary | Yes | Had the patient died within 28 days following discharge from NHS Trust hospital? 1 = Yes 0 = No | Site specific electronic patient record |
| 22 | Date of Death | Date dd.mm.yyyy | Yes | If the patient had died within 28 days following discharge from NHS Trust hospital, what is the date of death | Site specific electronic patient record |
| 23 | Immediate condition | Varchar | Yes | ICD code relating to the disease or condition directly relating to death | Site specific electronic patient record |
| 24 | Contributing condition | Varchar | No | ICD code relating to other significant conditions contributing to the death but not related to the disease or condition causing it | Site specific electronic patient record |

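### 28-day mortality is defined from CT acquisition, but the data dictionary's two death fields run from hospital discharge and, read literally, may omit deaths before discharge

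*Protocol*

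**What the plan says.** **The outcome.** Section 6.3 lists "Death within 28 days of NCCT head acquisition" among the secondary outcomes. Section 13.1 describes the linkage as concerning "death within 28 days of Head-NCCT acquisition date". Section 8.5 says that follow-up data "against outcomes will be collected 28 days after the Head-NCCT acquisition date". All three start the clock at the scan.

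**The fields that carry it.** In Appendix 5, 5.4.3, attribute 21 is a mandatory binary item: "Had the patient died within 28 days following discharge from NHS Trust hospital". Attribute 22, also mandatory, reads "If the patient had died within 28 days following discharge from NHS Trust hospital, what is the date of death". Both start the clock at discharge.

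**Related fields.**
- Attribute 23 is an "ICD code relating to the disease or condition directly relating to death", with no timing and no discharge condition.
- Attribute 17 is "Length of stay in hospital related to that admission", with no unit or start point stated.
- Attribute 8 in 5.4.1 is "The time of patient arrival to the Emergency Department".
- Attribute 4 in 5.4.2 gives the CT acquisition time.
- Attribute 16 in 5.4.3 is a discharge timestamp, but for leaving the ED. There is no timestamp for discharge from the hospital.

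**The concern.** The outcome and the fields meant to supply it have different time origins. Three things follow if the fields are filled in as worded.

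1. A patient who dies before discharge did not die after discharge, so attribute 21 is 0 and attribute 22 is empty. That death is part of the outcome.
2. For a patient discharged alive after the scan day, attribute 21 stays open beyond day 28 and picks up deaths that are not part of the outcome.
3. At the section 8.5 linkage, 28 days after acquisition, attribute 21 is still open for anyone discharged after the scan day, so it cannot yet be given a final 0.

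The first matters most. Discharge happens after the intervention, and section 6.5.1 expects qER to speed up treatment and referral. If the share of deaths that occur in hospital differed between the unaided and aided phases, recorded mortality would differ with no true change. The documents do not say whether that share will differ. Death is also listed as a data element for the health economic assessment (section 6.5.3), so the same fields may be used there.

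**Working it through.** The protocol gives no mortality figure, so there is none to reproduce. The check compares the two windows and then shows what the gap could do under stated assumptions.

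**Step 1: the windows.** Let day 0 be CT acquisition and L the number of days from acquisition to discharge.

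- Outcome (section 6.3): day 0 to day 28.
- Attributes 21 and 22: day L to day L + 28.
- Overlap: day L to day 28.

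The protocol gives no value for L, so those below are illustrative.

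| L (days) | Outcome and section 8.5 linkage close | Attribute 21 closes (L + 28) |
|---|---|---|
| 1 | 28 | 29 |
| 7 | 28 | 35 |
| 14 | 28 | 42 |
| 28 | 28 | 56 |

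**Step 2: what can be repaired from the listed fields.** Every post-discharge death within 28 days of acquisition is also within 28 days of discharge, so attribute 21 captures it. Attribute 22 minus the acquisition time then removes deaths after day 28. Deaths between day 0 and day L cannot be recovered from attributes 21 and 22. Attribute 23, together with ED arrival time and length of stay, might reveal some of them and an approximate date. No rule requires that derivation, and it yields no exact date.

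**Step 3: share of 28-day deaths recorded.** Let s be the share of 28-day deaths that occur before discharge. The documents do not give s. With literal coding and no recovery, the recorded share is 1 − s.

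- s = 0.25: 1 − 0.25 = 0.75
- s = 0.50: 1 − 0.50 = 0.50
- s = 0.75: 1 − 0.75 = 0.25

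**Step 4: effect on the phase comparison.** Assume equal true mortality in both phases and an s that is 0.05 lower in one of them. The ratio of recorded mortality is (1 − s + 0.05)/(1 − s).

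- s = 0.25: 0.80/0.75 = 1.067, an apparent relative rise of 6.7%
- s = 0.50: 0.55/0.50 = 1.10, a rise of 10%
- s = 0.75: 0.30/0.25 = 1.20, a rise of 20%

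The 0.05 difference is an assumption chosen to show sensitivity, not an expectation.

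**The case against.** The strongest reply is that the governing text is right and the table is a draft. Sections 6.3, 8.5 and 13.1 agree on acquisition as the origin. Sections 8.3 and 13.1 list date of death with no discharge condition. Both call the dictionary an example, and Appendix 5 (5.1 and 5.4) says that it depends on what each site holds and that the attribute list is not exhaustive. The mandatory column cannot be strictly literal either, since survivors have no date or cause of death. A site that records an in-hospital death as a discharge would capture it. This shows what was intended and makes total loss of in-hospital deaths less likely. It does not correct the two rows. The non-exhaustive clause allows further attributes to be derived from the listed ones, and an exact in-hospital death date cannot be. Nothing obliges the four sites to treat death as a discharge, or to do so alike.

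It is also fair to say that only the first of the three consequences reaches the outcome. Late deaths can be removed, and a patient known to be alive at day 28 after acquisition is a final negative for the outcome whatever attribute 21 says. That stands. The lost information is the deaths before discharge.

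The in-hospital shares and the 5-point phase difference are assumptions. That stands too, and the figures in steps 3 and 4 should be read only as a range.

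Finally, the source of attribute 21 is the site's patient record, and the documents do not say that this record captures deaths outside hospital. However, attribute 21 already asks for post-discharge deaths from that source, and section 8.5 already plans linkage at 28 days, so rewording creates no new dependency.

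**Conclusion.** The contradiction is explicit and should be fixed. The outcome runs from acquisition, while the only two fields that ask whether and when the patient died run from discharge. Used as written, they may leave deaths before discharge coded 0 and undated.

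The size of the omission cannot be computed from the documents. Under the assumed in-hospital shares of 25% to 75%, literal coding and no recovery, between 75% and 25% of 28-day deaths would be recorded. A 5-point phase difference in that share would then create an apparent relative difference of 6.7% to 20%.

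Confidence is high in the mismatch. How many deaths would actually be lost depends on site coding practice, which is not described. The effect is confined to one secondary outcome and any economic use of the same fields. The primary turnaround-time analysis and the sample size are untouched.

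**What to change.** Redefine attribute 21 as death from any cause, in or out of hospital, within 28 days of the CT acquisition time in 5.4.2. Redefine attribute 22 as the date of any such death, with no reference to discharge. The field then closes on the same day as the section 8.5 linkage, so no further follow-up is needed. Appendix 5, 5.3 has files arriving about every three months, which does not guarantee extraction at day 28; with an acquisition-based definition and a date, a later extraction gives the same answer. The cost is two dictionary rows, best changed before sites extract data.

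A separate editorial point carries no weight in the conclusion above. The synopsis ends the study after the last patient's 28-day follow-up, whereas section 10 ends it at month 13. Taking a month as 30.4375 days, 13 × 30.4375 = 395.7 days, and 395.7 − 28 = 367.7 days, or month 12.08. Follow-up would therefore fall short at the section 10 date only if scanning ran past about month 12.1. With 12 months of scanning there is no shortfall (365.25 + 28 = 393.25 days, below 395.7). One sentence in section 10 would align the two definitions. The protocol should also say what its 12-, 13- and 14-month durations each measure, since they may refer to different things and Figure 1, not visible here, may settle the scanning period.

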6.5.3 Health Economic Data

The data elements that will be used for the analysis of health economic assessment are listed below:

Intervention and comparator

- Numbers of ground truth positive and ground negative cases
- AI false positives, true positives, false negatives, true negatives

- AI output (+/- per disease)
- Radiologist output and/or agreement with AI decision per scan
- Time of admission to ED
- Time (with and without qER) of CT scan
- Time (with and without qER) time to ER physician viewing scan
- Time (with and without qER) to radiologist open scan
- Time (with and without qER) to radiologist report / close scan
- Time (with and without qER) ER physician opens report
- Time (with and without qER) to onwards referral
- Time (with and without qER) to treatment (need specific treatment per speciality pathway e.g. time to embolisation, time to surgery etc)
- Time to AI output delivered to PACS

Resource Use

- Number of head CTs performed out of hours
- Number of head CTs performed in hours
- Definition of in and out of hours per trust
- Reason for the scan (primary suspected diagnosis and/or main symptom)
- Death
- Reattendance to hospital with same presentation
- Transfer to other hospital
- Admission to same hospital, including care pathway
- Clinical diagnosis, including sub-type and severity of (e.g ASPECTS score for stroke, any relevant head trauma scales)
- False negative outcomes (e.g. missed diagnoses and severity)
- False positive outcomes (e.g. misdiagnosis and severity)
- Length of stay and wait in the ED
- Length of stay in hospital / wait to transfer

Costs

- AI implementation, maintenance, training, per scan costs
- Treatment cost per pathway/speciality (to be sourced from published literature)
- ED visit cost (to be sourced from published literature)
- Cost of hospital admission (to be sourced from published literature)
- Cost of hospital transfer (to be sourced from published literature)
- Cost by ward type (to be sourced from published literature)
- Cost of outsourcing CT head reading in and out of hours (to be sourced from published literature)

Utilities

- Will be applied to patient outcomes (values to be sourced from published literature)

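### 28-day death is promised by data linkage to an unnamed source, while the data dictionary takes it only from the site's own record with no code for untraced patients, so deaths elsewhere may be counted as survival

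*Protocol*

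**What the plan says.** Section 6.3 lists "Death within 28 days of NCCT head acquisition" among the secondary outcomes. Section 8.3 gives the method: "Data linkage for follow-up (death within 28 days of Head-NCCT acquisition date) against outcomes will be collected for 28 days". Sections 8.5 and 13.1 make the same promise. None of the three names a death register or any other linked source. The linking is given to the sites: "Evaluation sites will periodically collect, clean, link, de-identify and supply data in an agreed format". In section 8.3 date of death appears in a list introduced by "Extraction of routinely collected hospital data".

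Appendix 5, 5.4.3 defines the field itself. Item 21 reads "Death within 28 days following discharge | Binary | Yes", the last entry being the mandatory flag. Its coding and source are "discharge from NHS Trust hospital? 1 = Yes 0 = No | Site specific electronic patient record". Items 22 to 24 (date, immediate cause and contributing cause of death) carry the same source. The introduction to 5.4.3 says that in binary fields 0 stands for absence. No value is provided for unknown or not traced.

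The protocol also expects patients to leave the scanning site. Item 16 of the same table records leaving ED for a ward or for home, and section 6.5.3 lists "Transfer to other hospital" as a data item.

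**The concern.** The body of the protocol and the dictionary give different accounts of how a death is found. Linkage suggests that vital status is checked for every patient. The dictionary points only to what the scanning hospital's record holds, and offers two answers. A site that follows it has no defined way to separate a patient known to be alive at day 28 from one about whom nothing is known.

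At stake is the 28-day mortality outcome and, through section 6.5.3, the death input to the economic evaluation. Any deaths missed in both phases would lower reported mortality. If the missed share changed when qER went live, the comparison of phases would be distorted as well. The study hopes for faster referral and onward care, so a change in patient movement is conceivable. Later repair would be difficult, because section 8.1 has data anonymised before they reach the central team.

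**Working it through.** **Comparing the texts**

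- Method: linkage in 8.3, 8.5 and 13.1; extraction from the site's electronic record in Appendix 5, 5.4.3.
- Linked source: not named in the body. Appendix 5, 5.4 gives the origins of the schema as routine clinical data, the qER platform and the clinical fellow's report. No death register is among them.
- Coding: 1 or 0, with 0 meaning absence and no third value.
- Completeness: nothing states whether a site's record receives deaths that occur elsewhere. Appendix 5, 5.2 expects site data to differ, particularly between England and Scotland, so one answer cannot be presumed for all four sites.

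A death outside the site's view may therefore become a 0, but the text does not establish that it will.

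**Size, for illustration only**

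The protocol gives no mortality or transfer rate and no power calculation for death. The only figures available are the scan counts in section 15.1, which reproduce: 35 × 12 = 420 abnormal scans per site; 420 × 4 = 1,680; 1,680 / 0.10 = 16,800 scans in all.

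Let p be true 28-day mortality and u the share of deaths the site record does not hold. Both are assumptions. Observed mortality is p(1 − u), and missed deaths number n·p·u. With n = 1,680:

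- p = 10%: u = 10%, 30%, 50% gives observed 9%, 7%, 5%, and 16.8, 50.4, 84.0 deaths missed.
- p = 5%: u = 10% to 50% gives 8.4 to 42.0 missed.
- p = 20%: u = 10% to 50% gives 33.6 to 168.0 missed.
- u = 0: none missed.

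**Effect on the comparison of phases**

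- Equal u: the factor (1 − u) cancels from the risk ratio. The absolute difference shrinks by the share u. For a true 20% relative reduction at p = 10%, the difference falls from 2.0 points to 2.0 × 0.7 = 1.4 points at u = 30%. With no true effect, no difference is created.
- Unequal u and no true effect: the observed ratio is (1 − u aided)/(1 − u unaided). With 20% unaided and 30% aided it is 0.70/0.80 = 0.875. Reversed, it is 0.80/0.70 = 1.143. The direction is not known in advance.

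**Could a shift in patient movement dominate the comparison?**

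Spurious fall = (rise in share leaving) × (their mortality) × (share of those deaths unseen). Assume a 5-point rise, 20% mortality and 30% to 100% unseen: 5 × 0.20 × 0.30 = 0.3 points, up to 5 × 0.20 × 1.00 = 1.0 point. With equal phases and no clustering or calendar adjustment, the SE of a mortality difference is √(4p(1 − p)/n).

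- Among 1,680 abnormal scans at p = 10%: √(4 × 0.10 × 0.90/1,680) = 1.46 points. The fall is 0.3/1.46 to 1.0/1.46, about 0.2 to 0.7 SE.
- Across 16,800 scans at p = 5%: √(4 × 0.05 × 0.95/16,800) = 0.34 points. If only the roughly 10% abnormal scans shift, the fall is diluted to 0.03 to 0.10 points, about 0.1 to 0.3 SE.

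**The case against.** The strongest reply is that nothing shows the site record to be incomplete. Item 21 asks about death after discharge, and items 22 to 24 ask for its date and coded causes, so the dictionary presumes that the record holds events after the patient has left. The sites do the linking, and a site record updated from an outside source would satisfy both texts. This stands: a reader might infer that patients who die elsewhere are certain to be scored as survivors, or that a promised death register has been dropped, and the protocol supports neither.

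Nor does the mandatory flag force a 0. Items 19, 22 and 23 are also mandatory, although a patient in no other trial has no trial number and a survivor has no date or cause of death. A blank in item 21 is not excluded. That point stands too, but it leaves the meaning of a blank undefined.

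The dictionary is also called an example (8.3, 13.1), and Appendix 5, 5.1 says it can be produced only after each site's data have been analysed. This weakens the point without removing it. Section 13.1 attaches it as Appendix 5, 5.1 describes a dictionary as fixing what each site collects, and the additions foreseen in 5.4 are derivations from listed attributes. A death that was never captured cannot be derived.

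Finally, faster reporting may change when patients move without changing how many have left by day 28. That is fair, and differential bias remains a possibility only.

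**Conclusion.** The point holds as an unresolved ambiguity in how a secondary outcome is ascertained. Linkage is promised without a source, the dictionary names only the site record, and no code separates untraced from alive. Deaths elsewhere may therefore be counted as survival unless each site's record is fed by a death source.

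If that happens, 28-day mortality is understated in proportion to the unseen share. A spurious difference between phases needs that share to differ by phase. The document supplies none of the rates, so every size shown rests on assumption, and zero bias is among the possibilities.

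A reader might take the 5-point shift, apply it to all 16,800 scans and infer a bias of 1 to 3 SE (0.3/0.34 to 1.0/0.34). That is not supported. qER prioritises flagged scans, and section 15.1 assumes about 10% of scans are abnormal, so if only those are affected the shift among them would have to be 5/0.10 = 50 points. A 5-point shift within them is below 1 SE, and clustering and calendar adjustment would normally widen the SE further. The primary turnaround-time analysis does not depend on this field.

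**What to change.** - In 8.3 and 8.5, name the death source to be linked.
- Give that linked source for items 21 to 24, at all sites and in both phases, with matching done before de-identification.
- Add a code for *vital status not confirmed at day 28*, so that an untraced patient is missing and not alive.
- Where a site cannot link, report its outcome as *death recorded at the scanning site within 28 days* and do not present it as 28-day mortality.

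Items 21 and 22 also count the 28 days from discharge, whereas 6.3 and 8.3 count from acquisition. That is a separate contradiction, which the same edit should reconcile.

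The cost is a dictionary change, one trace per site, possibly an update to the site data agreements, and a short wait for registered deaths.
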